### **4.5.2. Adverse Events**

All AEs will be coded using the MedDRA coding system (Version 24.0 or later) and displayed in tables and data listings by SOC and PT. Adverse events will also be graded using the National Cancer Institute Common Terminology Criteria for AEs (NCI-CTCAE) on a scale of Grades 1 to 5 in which Grade 1 is a mild AE, Grade 2 a moderate AE, Grade 3 a severe AE, Grade 4 a life-threatening or disabling AE, and Grade 5 a fatal AE). Those not listed by CTCAE will be graded as either mild, moderate, or severe.

Analyses of AEs will be performed for those events that are considered treatment-emergent, where treatment-emergent is defined as any AE with onset after the administration of randomized study medication at the start of the Run-in period through the end of the study (at the end of the 3-week follow-up period), any event that was present at baseline (beginning of Run-in period) but worsened in intensity or was subsequently considered drug-related by the Investigator through the end of the study, or any event deemed to be related to study drug exposure.

The number and percentage of patients with any treatment-emergent adverse event (TEAE), with any TEAE assessed by the Investigator as related to treatment (definite, probable, or possible relationship), with any serious TEAE, any serious related TEAE, with any TEAE resulting in study drug withdrawal, with any TEAE leading to death will be summarized by QD/QW treatment group and overall. All TEAE analyses will have separate tabulations for two time frames: the beginning of the randomized, double-blind period (Day 1) to Week 14 and the beginning of the Run-in period through the end of the 3-week follow-up period (end of study). Since visits are not collected for AEs, the dates that each patient started and ended treatment at

each of these periods will be used to compare to the AE start and end dates for each patient in order to subset on the AEs specific to the randomized, double-blind period.

In these tabulations, each patient will contribute only once (i.e., the most related occurrence or the most intense occurrence) to each of the incidence rates in the descriptive analysis, regardless of the number of episodes.

No formal hypothesis-testing analysis of AE incidence rates will be performed.

All AEs occurring on study will be listed in patient data listings. By-patient listings also will be provided for the following: patient deaths, serious TEAEs, serious related TEAEs, TEAEs leading to withdrawal, TEAEs related to the drug, and TEAEs of CTCAE Grade 3 or higher.

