3.2. Setmelanotide Benefit/Risk Assessment

In patients with RGDO, setmelanotide has been associated with clinically meaningful reductions in weight and improvement in hunger. In particular, in patients with POMC or LEPR deficiency obesity, who are characterized by early-onset obesity, severe hunger and progressive weight gain, setmelanotide has demonstrated clinically meaningful and statistically significant weight reduction, often bringing patients with very high morbid obesity body mass index (BMI) (>40 kg/m²) to BMI ranges in the overweight or normal range (<30 kg/m²). In addition to weight loss, setmelanotide has demonstrated clinically meaningful and statistically significant decreases in hunger. Both the decreased hunger and the weight loss continued over 52 weeks of treatment and are maintained with continued setmelanotide treatment. Furthermore, following the significant weight loss with setmelanotide treatment, there were improvements in lipids and other parameters, as well as body composition with decreased fat mass and decreased waist circumference. These weight loss changes were accompanied by improvements in quality of life.

Setmelanotide is well tolerated. Side effects of setmelanotide are predictable, well understood, and do not present significant safety concerns. Collectively, safety data obtained to date show that adverse events (AEs) commonly associated with setmelanotide include injection site reactions (ISRs) and skin hyperpigmentation. Less commonly, nausea and vomiting were reported and rarely, sexual AEs have been observed. Potential mechanistic-based events such as hypertension have been assessed throughout the setmelanotide clinical development program and have not been observed. Events associated with severe obesity such as depression and suicidal ideation occurred infrequently and were assessed as not related to setmelanotide.

Specifically, regarding children less than 12 years old, the AEs reported in this population were consistent with those reported in other studies of setmelanotide. Adverse events reported as related to setmelanotide treatment were consistent with the known safety profile. No evidence for concern regarding bone development has been observed.

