8.8.11.1. Time Period and Frequency for Collecting AE and SAE Information

All AEs, including SAEs, will be collected from the start of the Run-in Period to the end-of-trial visit (Week 30). AEs reported after starting the Run-in Period will be considered treatment-emergent AEs.

Medical occurrences that begin before the start of the Run-in Period but after obtaining informed consent will be recorded on the Medical History/Current Medical Conditions section of the eCRF not the AE section.

All SAEs will be recorded and reported to the Sponsor or designee within 24 hours from the point in time when the Investigator becomes aware of the SAE. All SAEs must be reported whether or not considered causally related to the study drug. The Investigator will submit any updated SAE data to the Sponsor within 24 hours of it being available.

Investigators are not obligated to actively seek AEs or SAEs in former trial patients. However, if the Investigator learns of any SAE, including a death, at any time after a patient has been discharged from the trial, and he/she considers the event to be reasonably related to the trial treatment or trial participation, the Investigator must promptly notify the Sponsor.

The method of recording, evaluating, and assessing causality of AE and SAE and the procedures for completing and transmitting SAE reports are provided in Appendix 3.

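### SAP 4.5.2 does not reliably isolate adverse events that began or worsened after the first randomized dose, so the Day 1 to Week 14 TEAE table may be diluted or incomplete

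*SAP*

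**What the plan says.** SAP 4.5.2 has three routes by which an event becomes treatment-emergent:

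1. "onset after the administration of randomized study medication at the start of the Run-in period", running to the end of the trial.
2. "any event that was present at baseline (beginning of Run-in period) but worsened in intensity or was subsequently considered drug-related by the Investigator".
3. "or any event deemed to be related to study drug exposure".

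The results are tabulated twice: "All TEAE analyses will have separate tabulations for two time frames: the beginning of the randomized, double-blind period (Day 1) to Week 14", and again from Run-in to the end of follow-up. AE records carry no visit, so the SAP says that each patient's treatment start and end dates for "each of these periods will be used to compare to the AE start and end dates for each patient". Its stated aim is to pick out the events that belong to the double-blind phase. Within a table, "each patient will contribute only once (i.e., the most related occurrence or the most intense occurrence) to each of the incidence rates".

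Protocol 8.8.11.1 collects AEs from the start of Run-in. It adds: "Medical occurrences that begin before the start of the Run-in Period but after obtaining informed consent will be recorded on the" medical history page instead of the AE page. Protocol 3.2 says that the effects "commonly associated with setmelanotide include injection site reactions (ISRs) and skin hyperpigmentation". Protocol 6.1 requires at least 6 months on QD setmelanotide before entry.

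**The concern.** Safety of the weekly formulation is the secondary objective, and the Day 1 to Week 14 table is the only TEAE table that compares randomized groups. In the full-study table, the group labelled QD also contains 13 weeks of open-label QW (SAP 3.5).

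That table should show what began or got worse on randomized QD or QW, and three features of SAP 4.5.2 work against this.

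- **Entry without onset or worsening.** Routes 2 and 3 let an unchanged event in once it is called related.
- **Wrong anchor.** Route 1 refers to randomized medication in Run-in, but every patient takes QD then and randomization is on Day 1. The reference state is the start of Run-in for both tables.
- **Start and end dates.** A rule that really uses the end date will either admit events that began on Run-in QD or lose events that have not resolved by Week 14.

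Background events counted in both arms pull the two incidences together, which is the direction of the comparability hypothesis in Protocol 3.2. Dropping unresolved events removes the most persistent ones. Because persistence can depend on the assigned formulation, randomization does not balance that loss.

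**Working it through.** The plan states no event rate, power or margin for safety, so there is no figure to reproduce. The check has two parts.

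**1. The date rule applied to four example events.** Protocol Table 1 puts the first randomized dose on Day 1 and the Week 14 visit, where open-label QW starts, on Day 92. The double-blind period is therefore taken as Days 1 to 91. The SAP does not say how the dates are to be compared; three readings are possible.

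| Event | Onset in period | Overlap with period | Wholly inside period |
|---|---|---|---|
| A. Unchanged effect from the extension trial, ongoing, called related (if recorded as an AE) | out | in | out |
| B. Onset Day -5 (Run-in), ends Day 10 | out | in | out |
| C. Onset Day 40, ends Day 60 | in | in | in |
| D. Onset Day 85, ends Day 120 | in | in | out |

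Overlap admits A and B, which began before randomization. Full containment loses D, a new event on blinded drug. Only the onset reading gives the right answer for all four, and under it the end date plays no part. Event B also meets the treatment-emergent definition, because nothing in that definition resets to Day 1.

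**2. What counted carry-over does to the any-TEAE comparison.** Let p be the true share of patients with a new event in an arm. Let b be the share with a counted pre-Day 1 event, assumed equal in both arms and independent of new events. Each patient counts once, so:

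- observed share = 1 - (1-b)(1-p)
- observed difference = (1-b) × (p_QW - p_QD)

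Illustration with assumed true rates of 20% (QD) and 50% (QW), a difference of 30 points and a ratio of 2.50:

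| b (assumed) | QD observed | QW observed | Difference | Ratio |
|---|---|---|---|---|
| 10% | 1 - 0.9×0.8 = 28% | 1 - 0.9×0.5 = 55% | 27 points | 1.96 |
| 20% | 1 - 0.8×0.8 = 36% | 1 - 0.8×0.5 = 60% | 24 points | 1.67 |
| 40% | 1 - 0.6×0.8 = 52% | 1 - 0.6×0.5 = 70% | 18 points | 1.35 |
| 60% | 1 - 0.4×0.8 = 68% | 1 - 0.4×0.5 = 80% | 12 points | 1.18 |

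With assumed true rates of 10% and 30%, b = 40% gives 46% against 58%: 12 points instead of 20. About 30 patients randomized 1:1 gives about 15 per arm, so chance imbalance in b is also possible.

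**Two related loose ends.** SAP 3.10 codes a missing onset date to the day of treatment without saying whether that is the first Run-in dose or Day 1. Relatedness opens routes 2 and 3, yet SAP 4.5.2 uses definite, probable or possible, while Protocol Appendix 3 records only related or not related.

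**The case against.** A reader might infer that long-standing hyperpigmentation from the extension trial will be counted in every patient who has it, and that the randomized table therefore fails to measure what emerged. The documents do not support that.

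- TEAEs are drawn from recorded AEs. Protocol Appendix 3 does not treat ordinary fluctuation of a pre-existing condition as an AE unless it worsens, and Protocol 8.8.11.1 sends occurrences between consent and Run-in to medical history. A known, unchanged effect should mostly stay out of the AE data.
- The SAP commits to neither overlap nor containment, and its stated aim points towards events of the double-blind phase. Events with onset in Days 1 to 91 are counted under two of the three readings.
- Injection site evaluations are summarized by visit and treatment received (SAP 4.5.3), without the treatment-emergent definition. All AEs are listed by patient, so early onsets would be visible among about 30 patients.
- The dilution formula applies to any TEAE. In the tables by preferred term, an old event under one term does not hide a new event under another.
- Carry-over comes from the same earlier QD treatment and is balanced in expectation.

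These points reduce the concern without removing it. The medical-history rule names only occurrences after consent and does not touch Run-in onsets. Appendix 3 also counts as an AE a condition first detected after dosing even if it was there before. The SAP's schedule marks AE assessment at Screening, where the protocol's does not. A stated aim is not a rule that can be programmed, and equal carry-over is exactly what shrinks a difference.

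**Conclusion.** The point holds in a limited form. As written, SAP 4.5.2 does not reliably isolate events that began or worsened after the first randomized dose. The main exposure is to Run-in-onset events still open on Day 1, pre-existing conditions first recorded after dosing, and, under a containment reading, new events unresolved at Week 14.

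The size is unknown. The documents give neither event rates nor a carry-over share, and every rate and value of b in the illustration is an assumption. The protocol's AE rules suggest that b is towards the low end; at b = 10%, nine tenths of the difference remains. What does not depend on those assumptions is that the definition admits events on attribution alone and that the choice of date reading changes which events are counted.

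This should be fixed but is not critical: PK is primary, the safety analysis is secondary and descriptive, and no AE rates are tested.

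**What to change.** Reword SAP 4.5.2 before unblinding:

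- **Double-blind table:** count only AEs with onset, or worsening over the Day 1 state, from the first randomized dose to before the Week 14 open-label dose. Assign by onset or worsening date, never by end date.
- **Full-study table:** count onset or worsening from the first Run-in dose.
- Delete the word *randomized* from the Run-in clause.
- Delete the two attribution-only clauses, or confine the events they catch to a listing.
- List separately the events ongoing at Day 1.
- In SAP 3.10, state which day of treatment is used for imputed onset dates.
- Align the relatedness categories with Protocol Appendix 3, and the Screening mark for AE assessment with the protocol's schedule.

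The cost is SAP text only, with no new data. The downside is that slightly fewer related TEAEs are tabulated; they remain in the listings.

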#### 4.5.3. Injection Site Evaluations

Injection site evaluations will be summarized for all visits over time by QD/QW treatment received according to severity (none, mild, moderate, severe), and type of reaction (erythema, edema, induration, itching, pain or tenderness, or other reaction). For patients reporting more than one occurrence of the same type of reaction, the most severe reaction will be included in the summary.

A by-patient listing will be provided for all injection site evaluations and will also include measurement (if applicable).

#### 4.5.4. Laboratory Data

Clinical laboratory values will be expressed in the International System of Units.

The actual value and change from baseline to each on-study evaluation will be summarized for each continuous clinical laboratory parameter by visit and QD/QW treatment received. Categorical results will be summarized by counts and percentages of patients in each category. In the event of repeat values, the last non-missing value per study day/time will be used. Clinical laboratory parameters include:

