8.8.5. Laboratory Assessments

Blood and urine samples for clinical laboratory tests are to be collected after patients have been fasting for 8 hours. Samples are to be collected prior to setmelanotide administration.

The Investigators will adhere to the site-specific blood volume limits for safety laboratory and PK analyses to ensure minimal distress to pediatric patients. Due to the age of the children potentially eligible for participation in this trial, it may not be possible to collect all labs at every trial visit in this patient population, though efforts should be made to collect as many PK samples per protocol. Screening may be completed over multiple days to complete the required assessments. Venipuncture reduction is allowed should a patient experience unacceptable discomfort as deemed by the Investigator. After enrollment, if not all lab tests are possible, then the tests should be collected in the following descending order of priority: safety, anti-drug antibodies, trough PK, hemoglobin A1c, and then lipid panel.

All clinically significant laboratory abnormalities will be followed-up by repeat testing and further investigated according to the judgment of the Investigator.

The routine clinical laboratory parameters to be evaluated are as follows:

Hematology

Complete blood count with platelet count and standard indices will be obtained.

Chemistry

Sodium, potassium, chloride, carbon dioxide, albumin, total protein, glucose, blood urea nitrogen, creatinine, uric acid, aspartate aminotransferase, alanine aminotransferase, gamma-

glutamyltranspeptidase, creatine phosphokinase, alkaline phosphatase, total bilirubin, direct bilirubin, lactate dehydrogenase, calcium and phosphorus.

Coagulation Profile

Prothrombin time or international normalized ratio, and partial thromboplastin time, also referred to as activated partial thromboplastin time.

Urinalysis

Urine pH, glucose, protein, ketones, bilirubin, blood, urobilinogen, specific gravity, nitrite, and leukocytes by dipstick analysis or machine urinalysis. Urine microscopic examination will be performed if positive findings on dipsticks warrant further examination.

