### *Urinalysis*

Urine pH, glucose, protein, ketones, bilirubin, blood, urobilinogen, specific gravity, nitrite, and leukocytes by dipstick analysis or machine urinalysis. Urine microscopic examination will be performed if positive findings on dipsticks warrant further examination.

The frequency of patients with abnormal safety laboratory results will be tabulated by treatment received.

Shift tables of change in CTCAE grade of laboratory parameters from baseline to worst on-study values will be presented for hematology and clinical chemistry by QD/QW treatment received, if applicable. Shift tables of urinalysis results will be provided.

All laboratory data, including pregnancy test results, will be provided in data listings. A subset listing will be presented for all clinically significant laboratory values.

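### SAP 4.5.4 keeps the last of repeated laboratory values without exempting the abnormality counts or the worst-grade shift, so a repeat prompted by an abnormal result may replace that result in those tables

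*SAP*

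**What the plan says.** SAP 4.5.4 (Laboratory Data) opens with the by-visit summaries: "The actual value and change from baseline to each on-study evaluation will be summarized for each continuous clinical laboratory parameter by visit and QD/QW treatment". A sentence on counts and percentages for categorical results follows, and then the repeat rule: "In the event of repeat values, the last non-missing value per study day/time will be used". The rule names no table to which it is limited, and the SAP does not define study day/time.

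After the parameter lists, the same section plans two further tables:

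- An abnormality count: "The frequency of patients with abnormal safety laboratory results will be tabulated by treatment received".
- A worst-grade shift: "Shift tables of change in CTCAE grade of laboratory parameters from baseline to worst on-study values will be presented for hematology and clinical chemistry".

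Neither carries a statement about repeats. The section also provides listings: "All laboratory data, including pregnancy test results, will be provided in data listings", and "A subset listing will be presented for all clinically significant laboratory values".

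Protocol 8.8.5 says what prompts a repeat: "All clinically significant laboratory abnormalities will be followed-up by repeat testing and further investigated according to the judgment of the Investigator". It gives no timing for the retest.

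**The concern.** A last-value rule does little harm when repeats happen for reasons unrelated to the result. Here the protocol makes a repeat mandatory because the result was abnormal. The value most likely to be superseded is therefore the one a safety table is meant to show.

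For by-visit means this is a matter of convention. For a count of patients with any abnormal result, and for a shift to the worst value, it is not: if only last values enter, the shift reports the worst of the last values. Two programmers could also build different tables from the same data, because neither the scope of the rule nor the meaning of day/time is stated.

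Safety of the weekly formulation is the trial's secondary objective. About 30 patients are planned with 1:1 randomization, so roughly 15 per arm. One patient dropped from an arm's abnormality count moves that arm's rate by 1/15, or about 7 percentage points.

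**Working it through.** The documents give no figure on this point, so there is none to reproduce.

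**Step 1: direction.** For any patient, the worst grade over a subset of the post-baseline values cannot exceed the worst grade over all of them. Keeping only the last of a set of repeats can lower the reported worst grade or leave it unchanged; it cannot raise it. If a retest is worse than the first value, the last-value rule keeps it and nothing is lost. Any post-baseline distortion therefore runs toward normal.

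**Step 2: when it happens.** Take one patient with Grade 3 on the first sample and Grade 0 on the retest, and apply the rule to the worst-grade table.

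| Timing of the retest | All values used | Last per day | Last per day and time |
|---|---|---|---|
| Same day, later clock time | 3 | 0 | 3 |
| Same day, same time (re-assay) | 3 | 0 | 0 |
| Later day | 3 | 3 | 3 |

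The first row depends on how day/time is read. The second loses the abnormal value under either reading. The third never does. SAP 3.11 agrees with the third row: unscheduled data stand in for a scheduled visit only when that visit is missing.

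**Step 3: how many patients.** Patients missed = N × q × s × r, and the share of abnormal patients missed = s × r. N = 30 is the planned enrollment. The rest are assumptions, not figures from the documents:

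- q, the share of patients with a clinically significant abnormality, at one draw each: 0.1 to 0.3.
- s, the share of those repeated on the same day: 0 to 0.5.
- r, the share of repeats that come back normal: 0.5 to 0.8.

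With the rule read as last per day and applied to both tables, the share missed is:

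- s = 0: 0%
- s = 0.1: 0.1 × 0.5 to 0.1 × 0.8 = 5% to 8%
- s = 0.25: 12.5% to 20%
- s = 0.5: 25% to 40%

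At q = 0.2 there are 30 × 0.2 = 6 abnormal patients, of whom 0 to 6 × 0.40 = 2.4 would be missed. At q = 0.1 the range is 0 to 1.2, and at q = 0.3 it is 0 to 3.6.

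**Step 4: how firm r is.** Assume normally distributed values, an upper limit at 1.96 SD and a test-retest correlation of 0.9, 0.8 or 0.6. The share of retests back inside the limit is then:

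| First value above | 0.9 | 0.8 | 0.6 |
|---|---|---|---|
| 1.96 SD | 41% | 56% | 75% |
| 3 SD | 2% | 15% | 50% |
| 4 SD | 0% | 1% | 24% |

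The more extreme the value that prompts the repeat, the smaller r becomes. At s = 0.5 and r = 0.02 the share missed is only 1%. For the graded shift, a return inside the limit is not the only loss: a fall from one grade to a lower one also changes the table.

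**Step 5: after the fix.** If every valid post-baseline value feeds both tables, the patient in step 2 is Grade 3 in all three rows, and the loss is 0 for any q, s and r.

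**The case against.** The strongest reply is that the rule was never meant for these two tables. It closes the paragraph on by-visit and categorical summaries; the count and the shift come later, and the shift has its own selection rule in the word worst. A specific rule would normally govern its own table. If day/time means day and clock time, a redraw later the same day is kept anyway. Same-day redraws may also be rare: Protocol 8.8.5 gives no retest timing and asks for fasting samples taken before setmelanotide. The listings keep every value. Protocol Appendix 3 makes abnormal results that the investigator considers clinically significant adverse events, and SAP 4.5.2 tabulates those.

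Much of this stands. A reader might infer that same-day retests delete abnormal values from the tables. The documents do not support that as a certainty, because it needs the broad reading of scope together with either the per-day reading of day/time or a repeat at the same recorded time. A reader might also infer that roughly half of retested abnormal values would disappear. That figure comes from first values anywhere beyond 1.96 SD, whereas the protocol's trigger is clinical significance.

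What does not stand is the idea that nothing needs saying. The rule follows a sentence on categorical results, so it is not plainly confined to means. Listings and adverse event records preserve individual cases but do not correct a summary labeled worst, and adverse event capture rests on investigator judgment. The preceding section, SAP 4.5.3, handles multiple injection site reactions by keeping the most severe; the laboratory section has no such statement for repeats.

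**Conclusion.** The point holds in conditional form. SAP 4.5.4 states a last-value rule, the protocol makes repeats depend on clinically significant abnormality, and no exception protects the abnormality count or the worst-grade shift. If the rule is applied to them, a same-day or same-time repeat may replace the abnormal value that prompted it. The effect runs only toward normal and conflicts with a table of worst on-study values.

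The size is unknown. Under the assumptions in the working it runs from none to 40% of patients with a clinically significant abnormality, with the lower end plausible because later-day retests are unaffected and more extreme values are less likely to normalize on repeat. This concerns secondary, descriptive safety tables; the primary pharmacokinetic analysis is untouched. It is a minor point, worth correcting because the correction is cheap. The documents give no ground for objecting to the last value in by-visit means, where first or last is a choice of convention.

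**What to change.** Amend SAP 4.5.4 in three places:

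1. Limit the last-value rule to the by-visit summaries.
2. State that all valid, non-missing post-baseline values, including repeats and unscheduled draws, feed the abnormality frequency and the CTCAE shift to worst. Exclude an invalid sample, such as a hemolyzed one, only on a documented laboratory flag.
3. Define study day/time, saying whether two draws on one day at different clock times count as repeats.

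The cost is a few sentences and a programming filter, with no new data, visits or patients. Reported abnormality rates may rise slightly. If the sponsor already intends to build the tables this way, the edit only records it.
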